8.1.2 Primary analysis of the co-primary efficacy variables

The co-primary efficacy variables for this study are PASI90 response and IGA response at Week 16, and the corresponding analyses are based on the RS. A subject will be classified as a PASI90 responder if the PASI score at Week 16 has improved at least 90% from Baseline, and IGA responder is any subject with a score of 0 or 1 (Clear or Almost Clear) with at least a 2-category improvement from Baseline to Week 16 in IGA score.

The primary analysis will be based on the stratified Cochran-Mantel-Haenszel (CMH) test where region and prior biologic exposure (yes/no) will be used as stratification variables.

For the assessment of noninferiority, a noninferiority margin of 10% will be used and evaluated based on the confidence interval for the stratified Cochran Mantel-Haenszel risk difference between bimekizumab and adalimumab. The Wald method will be used to calculate the confidence interval. A non-inferiority margin of 10% has been selected as this is considered to be a clinically relevant difference that could influence the choice of interventions used to treat chronic plaque PSO. Therefore, a difference within the 10% non-inferiority margin would suggest a similar impact on efficacy between the treatments.

The evaluation of superiority will use pairwise treatment comparisons based on the CMH test using the p-value for the general association. The odds ratio and associated confidence interval (CI) based on the Wald test will be presented. If one of the treatment groups has 0 or very low response where CMH can no longer be used, the logit method will be applied instead.

To calculate the stratified Mantel-Haenszel risk difference, the method of Greenland and Robins (1985) is used. For each combination of strata, a 2x2 table of treatment group and response is created. A theoretical 2x2 table for a given stratum is shown below, where $n = a+b+c+d$.

Treatment Group	Response	
	Yes	No
Bimekizumab	a	c
Adalimumab	b	d

Given that structure, the stratified Mantel-Haenszel risk difference, standard error, and two-sided $(1-\alpha)*100\%$ confidence interval may be written as follows:

$$RD_{MH} = \frac{\sum_i ((a_i * (b_i + d_i)/n_i) - (b_i * (a_i + c_i)/n_i))}{\sum_i ((a_i + c_i) * (b_i + d_i))/n_i}$$

$$SE_{MH} = \sqrt{\frac{\sum_i \left\{ \frac{[a_i * c_i * (b_i + d_i)^3] + [b_i * d_i * (a_i + c_i)^3]}{(a_i + c_i) * (b_i + d_i) * n_i^2} \right\}}{\left\{ \sum_i \left[\frac{(a_i + c_i) * (b_i + d_i)}{n_i} \right]^2 \right\}}}$$

$$CI_{MH} = RD_{MH} \pm \text{probit}(1 - (\alpha/2)) * SE_{MH}$$

For the assessment of non-inferiority of bimekizumab to adalimumab, the lower 97.5% confidence limit for the stratified Mantel-Haenszel risk difference will be considered. If that value is greater than -10%, then non-inferiority will have been established.

Non-responder imputation will be used to account for missing data in the primary analysis. Specifically, any subject who withdraws from IMP prior to Week 16 or who has missing data for the co-primary efficacy variables at the Week 16 time point will be considered as a non-responder.

The number and percentage of subjects who are PASI90 responders at Week 16 will be summarized. IGA response will be summarized in the same manner as PASI90 responder variable.

A line plot of the percentage improvement from Baseline in PASI score over time by treatment group will be produced.

By-subject listings of PASI and IGA responder variables, PASI and IGA data will be provided.

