Note that the non-inferiority testing procedure will be based on a 1-sided significance level of 0.025 and a non-inferiority margin of 10%. The power to demonstrate non-inferiority to adalimumab using the other assumptions described above is >99% for both PASI90 and IGA responses.

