4.5 Multiple comparisons/multiplicity

[figure not shown]
The statistical analysis of the co-primary efficacy variables and selected secondary efficacy variables will account for multiplicity and control the familywise Type I error rate at a 2-sided alpha level of 0.05 by using a fixed sequence testing procedure.

The hypotheses (H_1 , H_2 , H_3 , H_4 , H_5 , H_6 , H_7 , H_8 , H_9 , H_{10} , H_{11} and H_{12}) comparing bimekizumab vs. adalimumab will be tested at a 2-sided alpha level of 0.05.

The first 2 hypotheses (H_1 and H_2) will test whether bimekizumab is noninferior to adalimumab for the co-primary efficacy variables, PASI90 response at Week 16 and IGA response at Week 16. This evaluation of noninferiority will be tested at a 1-sided alpha level of 0.025 and will be based on a 1-sided 97.5% CI and a noninferiority margin of 10%. If noninferiority is achieved, the alpha will be passed to the next test in the sequence, allowing the testing procedure to proceed. The co-primary efficacy variables of PASI90 response at Week 16 and IGA response at Week 16 will then be evaluated for superiority relative to adalimumab at a 2-sided alpha level of 0.05, and testing will proceed only if superiority is achieved for both endpoints.

The hypotheses associated with the subsequent secondary efficacy endpoints are based on testing for superiority relative to adalimumab. See Figure 4-1 for details on this procedure.

Figure 4-1: Sequence of testing

Note: Calculations for H₁-H₉ are based on the combined Bimekizumab arms with the sample size of 300. * in H₁₀-H₁₂ indicated calculations are based on the Bimekizumab Q4W/Q4W arm only with sample size of 150.

BKZ=bimekizumab; H=hypothesis; IGA=Investigator's Global Assessment; PASI=Psoriasis Area Severity Index; Q4W=every 4 weeks

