8 EFFICACY ANALYSES

The following sentence was added:

Additional summaries through the initial and maintenance treatment period will be produced for subjects who received bimekizumab from Week 24 onwards (BKZ week 24 set) in all three randomized treatment groups.

And

In addition, for subjects who started with adalimumab and switched treatment at the Week 24 Visit, change from Baseline (at Week 24) will be evaluated from Week 28 to Week 56 (see Section 3.2).

Was changed to:

In addition, for subjects who started with adalimumab and switched treatment at the Week 24 Visit, change from Baseline (at Week 24) will be evaluated from Week 28 to Week 56 **for PASI score and DLQI score only** (see Section 3.2).

Change #21

Section 8.1.1 Derivations of co-primary efficacy variables

The following text was added:

For missing PASI and IGA assessments at Week 16, available data from all visits (unscheduled or scheduled but without a planned assessment) within the 3 days window will be included.

Change #22

Section 8.1.2 Primary analysis of the co-primary efficacy variables

The following text in bold was added:

For the assessment of noninferiority, a noninferiority margin of 10% will be used and evaluated based on the confidence interval for the stratified Cochran Mantel-Haenszel risk difference between bimekizumab and adalimumab. The Wald method will be used to calculate the confidence interval. A non-inferiority margin of 10% has been selected as this is considered to be a clinically relevant difference that could influence the choice of interventions used to treat chronic plaque PSO. Therefore, a difference within the 10% non-inferiority margin would suggest a similar impact on efficacy between the treatments.

The evaluation of superiority will use pairwise treatment comparisons based on the CMH test using the p-value for the general association.

The odds ratio and associated confidence interval (CI) based on the Wald test will be presented. **If one of the treatment groups has 0 or very low response where CMH can no longer be used, the logit method will be applied instead.**

To calculate the stratified Mantel-Haenszel risk difference, the method of Greenland and Robins (1985) is used. For each combination of strata, a 2x2 table of treatment group and response is created. A theoretical 2x2 table for a given stratum is shown below, where $n = a+b+c+d$.

Treatment Group	Response	
	Yes	No
Bimekizumab	a	c
Adalimumab	b	d

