Given that structure, the stratified Mantel-Haenszel risk difference, standard error, and two-sided $(1-\alpha)*100\%$ confidence interval may be written as follows:

$$RD_{MH} = \frac{\sum_i ((a_i * (b_i + d_i) / n_i) - (b_i * (a_i + c_i) / n_i))}{\sum_i ((a_i + c_i) * (b_i + d_i) / n_i)}$$

$$SE_{MH} = \sqrt{\frac{\sum_i \left\{ \frac{[a_i * c_i * (b_i + d_i)^3] + [b_i * d_i * (a_i + c_i)^3]}{(a_i + c_i) * (b_i + d_i) * n_i^2} \right\}}{\left\{ \sum_i \left[\frac{(a_i + c_i) * (b_i + d_i)}{n_i} \right] \right\}^2}}$$

$$CI_{MH} = RD_{MH} \pm \text{probit}(1 - (\alpha/2)) * SE_{MH}$$

For the assessment of non-inferiority of bimekizumab to adalimumab, the lower 97.5% confidence limit for the stratified Mantel-Haenszel risk difference will be considered. If that value is greater than -10%, then non-inferiority will have been established.

Change #23

Section 8.2.3 Sensitivity analyses of the secondary efficacy variables

The following text was added:

It was noted during the conduct of the study that approximately 25 subjects received incorrect Placebo/Active treatment at Visit 20. All subsequent treatments were administered per protocol. The main analyses of the endpoints at Week 24 will include all subjects in the RS, however the potential impact of this on the Week 24 secondary endpoints (PASI90, PASI100 and IGA response) will be assessed through sensitivity analyses excluding these subjects from the analysis population.

Change #24

Section 8.3 Statistical analysis of other efficacy variables

By visit summaries will include the bimekizumab and adalimumab treatment groups. There will be 2 key approaches for understanding the data after Week 24:

- Summary of data for the RS through Week 56 based on randomized treatment group including bimekizumab Q4W, bimekizumab Q4W/Q8W and bimekizumab total. The adalimumab group will only be summarized up to Week 24
- Summary of Maintenance treatment period data among responders only for PASI90, PASI100, IGA (0/1), and DLQI respectively;
 - For Week 16 responders in bimekizumab Q4W, bimekizumab Q8W and bimekizumab total
 - For Week 24 responders in ADA/BKZ arm

Has been changed to

By visit summaries will include the bimekizumab and adalimumab treatment groups. There will be some key approaches for understanding the data after Week 24:

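### Does SAP 8.1.2 square the stratum weights in the wrong place, so that the interval deciding non-inferiority is about twice too wide?

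*SAP*

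**What the plan says.** SAP Section 8.1.2 defines the risk difference stratum by stratum, from 2x2 tables with a and c as bimekizumab responders and non-responders and b and d as the same for adalimumab. It states that "the method of Greenland and Robins (1985) is used" and then writes out the estimate, its standard error and the interval. In the standard error, the sum in the denominator reads "i \left[\frac{(a_i + c_i) * (b_i + d_i)}{n_i} \right]^2", with a further pair of braces around the whole sum.

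For the decision, "the lower 97.5% confidence limit for the stratified Mantel-Haenszel risk difference will be considered", and it must exceed -10%. SAP Section 4.5 adds: "This evaluation of noninferiority will be tested at a 1-sided alpha level of 0.025". Once non-inferiority is shown, the same endpoints are "evaluated for superiority relative to adalimumab at a 2-sided alpha level of 0.05"; Section 8.1.2 takes that p-value from the CMH general-association test.

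The formula appears a second time. SAP Section 13.1, Amendment 1, Change #22, introduced by "The following text in bold was added", shows Section 8.1.2 as amended. There the same denominator reads "i \left[\frac{(a_i + c_i) * (b_i + d_i)}{n_i} \right] \right\}^2", with the exponent on the outer brace.

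On power, SAP Section 2.4 says: "The power to demonstrate non-inferiority to adalimumab using the other assumptions described above is >99% for both PASI90 and IGA responses".

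**The concern.** The estimate is a weighted mean of stratum differences, so its variance has to be divided by the square of the summed weights. Dividing by the sum of squared weights gives the same answer only with one stratum. This plan has eight (four regions by prior biologic exposure), or six if Asia/Australia and Western Europe are merged under SAP Section 3.7.

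The interval is the gate for H1 and H2, and so for the whole fixed sequence. If the program followed the printed form, risk-difference intervals could include zero beside a very small CMH p-value. The non-inferiority step could also fail in a trial where superiority is significant.

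**Working it through.** **Inputs.** Rates of 75% vs 50% (PASI90) and 85% vs 68% (IGA), with 300 vs 150 subjects (SAP 2.4). Margin 10 points, one-sided 0.025 (SAP 4.5, 8.1.2). Strata: region by prior biologic exposure (SAP 8.1.2). Up to 30% biologic-exposed (Protocol 5.1), taken here as 30/70. Region shares are not given and are assumed.

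**1. The plan's own power.** Unstratified standard errors:
- PASI90: √(0.75×0.25/300 + 0.50×0.50/150) = 0.0479
- IGA: √(0.85×0.15/300 + 0.68×0.32/150) = 0.0433

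Non-inferiority power is Φ((difference + 0.10)/SE − 1.96):
- PASI90: Φ(0.35/0.0479 − 1.96) = Φ(5.35), above 99.99%
- IGA: Φ(0.27/0.0433 − 1.96) = Φ(4.28), about 99.999%

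Both agree with the stated figure of more than 99%. Superiority power also reproduces: 99.95% for PASI90, and 97.5% to 98.2% for IGA depending on the variance used, against the stated 97%.

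**2. Which denominator is right.** Write n1 = a+c, n0 = b+d and w = n1·n0/n. Then RD = Σ w(a/n1 − b/n0) / Σ w, so Var(RD) = Σ w²v / (Σ w)², with v = ac/n1³ + bd/n0³. Multiplying out, w²v = (ac·n0³ + bd·n1³)/(n1·n0·n²). That is exactly the numerator printed in both copies. It belongs over (Σ w)², so the Change #22 form is correct.

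A simulation of 10,000 trials (PASI90, regions 30/20/40/10) agrees. The empirical SD of the estimate was 0.0478. The mean standard error was 0.0468 with the square outside the sum and 0.1118 with it inside.

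**3. Size if the printed form were applied literally.** The inflation is Σw/√Σw². With constant allocation, w is proportional to stratum share, so the factor is 1/√(Σ share²). For 30/70 exposure, 0.3² + 0.7² = 0.58.

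| Assumed region shares | Σ share² | Inflation |
|---|---|---|
| Four equal | 0.25×0.58 = 0.145 | 2.63 |
| 35/15/40/10 | 0.315×0.58 = 0.183 | 2.34 |
| 20/10/65/5 | 0.475×0.58 = 0.276 | 1.91 |

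Wider assumptions give 1.65 (three regions 20/70/10, exposure 20/80) to 2.83 (eight equal strata).

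The estimate itself would still vary with an SD of about 0.043 for IGA; only the reported interval would widen. Simulated IGA non-inferiority success would then be about 90% (equal regions), 97% (35/15/40/10) or 99.7% (20/10/65/5). PASI90 success would be 98.8% or more in these three splits.

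**4. With the square outside.** Expected lower limits are 0.25 − 1.96×0.0479 = +15.6 points and 0.17 − 1.96×0.0433 = +8.5 points, well clear of −10.

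**5. The two copies side by side.**
- The numerators are identical; the exponent in the denominator differs.
- The denominator of the risk difference also differs, by one closing parenthesis: before the division by n in 8.1.2, after it in Change #22.
- In 8.1.2 the outer braces enclose the sum but have no function. In Change #22 they carry the square.
- Amendment 2 (SAP 13.2) lists ten changes, none to Section 8.1.2.

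Two bracket-level differences in one block, plus braces left without a purpose, fit an exponent displaced when the equation was read from PDF better than a change of formula.

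**The case for a change.** The strongest counter-argument is that Section 8.1.2 is the operative text, that its formula is balanced and has a definite meaning, and that a programmer coding from it as it reads here would get the wrong standard error for the primary gate. The algebra and the inflation factors stand.

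Nor is the match with Change #22 guaranteed by the absence of a listed change. The current SAP differs from its Amendment 1 log elsewhere without an Amendment 2 entry: Section 8.2.3 gives about 24 misdosed subjects against 25 in Change #23, and the second early-response subgroup in Section 4.8 is set at Week 16 against Week 4 in Change #15. A real typing slip in the signed SAP therefore cannot be excluded from the text alone.

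That shows the source is worth a look, not that the plan is wrong. A difference between an amendment log and current text is not in itself an error. The section also fixes the method in words, by naming it and by defining the estimate as a weighted mean, and only the square outside the sum gives that estimate's variance. Nothing in the documents shows that the program used the other form. Even a literal application would be conservative: it makes non-inferiority harder to claim and does not inflate type I error. The CMH superiority p-value does not use this standard error.

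**Conclusion.** The concern does not hold as an error in the plan. It rests on the position of one exponent in an equation read from PDF, and the other copy of that equation, the named method, the idle braces and the shifted parenthesis nearby all point to the correct form. On that form the interval has the right width, with standard errors of 0.048 and 0.043, and the stated non-inferiority power of more than 99% stands for both endpoints.

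The factor of 1.9 to 2.6 (1.65 to 2.83 under wider assumptions) describes only what a literal application would do, and it depends on region shares that the documents do not give. The conclusion assumes that the analysis follows the method named in Section 8.1.2. Comparing the signed PDF and the program with the Change #22 formula would settle what the text alone cannot; if they agree, no result changes.

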8.1.3 Sensitivity analyses of the co-primary efficacy variables

The following sensitivity analyses for the co-primary efficacy variables will be performed to evaluate the assumptions related to the handling of missing data:

8.1.3.1 Sensitivity Analysis #1

Missing data will be addressed by using MI (Markov-Chain Monte Carlo [MCMC] method for intermittent missing data, followed by monotone regression for monotone missing data, see

Section 4.2.1.6 to evaluate the effect of the method for handling missing data on the analysis. The actual PASI/IGA scores will be imputed and then dichotomized to obtain the response status. The treatment differences for each imputed data set will subsequently be evaluated using the stratified CMH test as used in the primary analysis. The results from each of the imputed data sets will be combined for overall inference using Rubin's rules, which account for the uncertainty associated with the imputed values (Rubin, 1987). This will be done using SAS PROC MIANALYZE. This procedure assumes a missing at random (MAR) pattern of missingness and corresponds to an estimand of the difference in outcome improvement if all subjects tolerated or adhered to treatment (Mallinckrodt et al, 2012). This is an estimand of efficacy to evaluate the de jure hypothesis.

8.1.3.2 Sensitivity Analysis #2

This sensitivity analysis will be based on observed data at Week 16. Subjects with missing data or who have prematurely discontinued IMP will be treated as missing (see Section 4.2.1.6). The same stratified CMH test as in the primary efficacy analysis will be used.

8.1.3.3 Sensitivity Analysis #3

The primary efficacy analyses from Section 8.1.2 will be repeated using LOCF as the imputation method (see Section 4.2.1.5).

8.1.3.4 Sensitivity Analysis #4

The primary efficacy analyses from Section 8.1.2 will be repeated based on the FAS and the PPS.

8.1.3.5 Sensitivity Analysis #5

As a sensitivity analysis to the primary analysis method, logistic regression based on the RS will be used. The odds ratio of the responder rates at Week 16 will be estimated and tested between treatment groups using a logistic regression model with factors of treatment group, region, and prior biologic exposure (yes/no). The odds ratio, associated confidence interval (CI), and p-value based on the Wald test will be presented. If the logistic regression model is unable to converge, then prior biologic exposure may be dropped from the model to facilitate convergence. If the model is still unable to converge, then region may be removed from the model as well. In addition, if the logistic regression model cannot converge, then Fisher's exact test will be used for inferential comparisons. As with the primary analysis, missing data will be handled using NRI.

8.1.3.6 Sensitivity Analysis #6

The center-by-treatment interaction will be tested by replacing region with center in the logistic regression model described in Section 8.1.3.5 and adding a center-by-treatment interaction term. In the model, center will be based on the original centers prior to pooling. However, if the model is unable to converge due to a low number of subjects at a given center, a pooling (see Section 3.7) will be described in order to allow the model to converge. In order to obtain reasonable estimates of variability for a treatment arm at a given center, a minimum of 15 subjects will be considered acceptable for a center to be included in the model without pooling. Given the 1:1:1 randomization allocation scheme, this should provide a minimum of about 5 subjects in each treatment group. Centers with fewer than 15 subjects will be eligible for pooling. The pooling algorithm used is described in Section 3.7.

In order to achieve model convergence, other explanatory variables e.g. other prior biologic exposure may be dropped from the model as for the logistic regression with region.

If the center-by-treatment interaction is not found to be significant ($\alpha=0.10$), then no further analyses will be performed. On the other hand, if the interaction is significant, further analyses will be conducted to determine which center or centers may be the source of interaction. This will be done by running the logistic regression model (including the interaction term) where each center will be systematically removed from the model. This impact of a given center will be based on the change in the interaction p-value when that center is removed. The center or centers that appear to be driving the significant interaction effect will then be removed from the model to verify that conclusions remain the same with or without the influential center(s). This sensitivity analysis will be based on RS with NRI for missing data.

8.2 Statistical analysis of the secondary efficacy variables

8.2.1 Derivations of secondary efficacy variables

8.2.1.1 PASI100 Response at Week 16 and 24

A categorical response variable, PASI100 at Week 16 is defined to be equal to 1 if the percentage improvement from Baseline to Week 16 in the PASI scores is 100% and 0 if the percentage improvement from Baseline to Week 16 is less than 100%. This definition is introduced for the purpose of identifying subjects who respond to the treatment (1 = responder, 0 = non-responder). The definition of percentage improvement from Baseline is given in Section 8.1.1.1.

PASI100 at Week 24 will be summarized in the same manner as PASI100 at Week 16.

8.2.1.2 PASI75 Response at Week 4

A categorical response variable, PASI75 at Week 4 is defined to be equal to 1 if the percentage improvement from Baseline to Week 4 in the PASI scores is 75% or greater and 0 if the percentage improvement from Baseline to Week 4 is less than 75%. This definition is introduced for the purpose of identifying subjects who respond to the treatment (1 = responder, 0 = non-responder). The definition of percentage improvement from Baseline is given in Section 8.1.1.1.

8.2.1.3 PASI90 Response at Week 24 and 56

PASI90 response definition and derivation are outlined in Section 8.1.1.1 and Section 8.1.1.2, use the data for weeks 24 and 56 respectively.

8.2.1.4 IGA Response at Week 24 and Week 56

IGA response and IGA 5-point scale are outlined in Section 8.1.1.3, define at Weeks 24 and 56 respectively.

